9.1.7 Overdose of Investigational Medicinal Product

Excessive dosing (beyond that prescribed in the protocol and including overdose) should be recorded in source documents and in the Drug Accountability module of the eCRF. Any SAE or nonserious AE associated with excessive dosing must be followed as any other SAE or nonserious AE. These events are only considered AEs or SAEs if there are associated clinical signs and symptoms or if the act of taking the excess medicine itself is an AE or SAE (e.g., suicide attempt).

9.1.8 Safety Signal Detection

Selected data from this study will be reviewed periodically to detect as early as possible any safety concern(s) related to the IMP so that the DSMB, investigators, clinical study patients, regulatory authorities, and IRBs/IECs will be informed appropriately and as early as possible.

The Medical Monitor or medically qualified designee/equivalent will conduct an ongoing review of SAEs and perform ongoing SAE reconciliations in collaboration with the Sponsor's drug safety representative.

As appropriate for the stage of development and accumulated experience with the IMP, medically qualified personnel at the Sponsor may identify additional safety measures (e.g., AEs, vital signs, laboratory or ECG results) for which data will be periodically reviewed during the study. The DSMB will be informed as defined in the DSMB charter.

9.2 Serious Adverse Events

9.2.1 Definition of Serious Adverse Event

Once it is determined that a patient experienced an AE, the seriousness of the AE must be determined. An SAE must meet one or more of the following criteria:

- 1. Results in death.
- 2. Life-threatening.

Note: Life-threatening does not include a reaction that might have caused death had it occurred in a more severe form.

- 3. Significant or persistent disability/incapacity.
- 4. Congenital anomaly/birth defect (including that occurring in a fetus).
- 5. Important medical event that, based upon appropriate medical judgment, may jeopardize the patient and may require medical or surgical intervention to prevent one of the other outcomes listed in the definition of serious.

Note: Important medical events may include allergic bronchospasm requiring intensive treatment in an emergency room or at home, blood dyscrasias that do not result in inpatient hospitalization, or the development of drug dependency or drug abuse.

6. Initial inpatient hospitalization or prolongation of hospitalization.

Note: A patient admitted to a hospital, even if he/she is released on the same day, meets the criteria for the initial inpatient hospitalization. An emergency room visit that results in admission to the hospital would also qualify for the initial inpatient hospitalization criteria. However, emergency room visits that do not result in admission to the hospital would not qualify for this criteria and, instead, should be evaluated for one of the other criteria in the definition of serious (e.g., life-threatening adverse experience, important medical event).

Hospitalizations for reasons not associated with the occurrence of an AE (e.g., preplanned surgery or elective surgery for a preexisting condition that has not worsened or manifested in an unusual or uncharacteristic manner) do not qualify for reporting. For example, if a patient has a condition recorded on his/her medical history and later has a preplanned surgery for this condition, it is not appropriate to record the surgery or hospitalization as an SAE, since there is no AE upon which to assess the serious criteria. Please note that, if the preexisting condition has worsened or manifested in an unusual or uncharacteristic manner, this would then qualify as an AE and, if necessary, the seriousness of the event would need to be determined.

Note: The term "severe" is often used to describe the intensity (severity) of a specific event (as in mild, moderate or severe myocardial infarction); the event itself, however, may be of relatively minor medical significance (such as severe headache). This is not the same as "serious," which is based on patient/event outcome or action criteria usually associated with events that pose a threat

to a patient's life or functioning. Seriousness (not severity) serves as a guide for defining regulatory reporting obligations.

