- 5. Is a congenital anomaly or birth defect, i.e., an adverse event (AE) that occurs in the child or fetus of a patient exposed to a study drug prior to conception or during pregnancy.
- 6. Is an important medical event, i.e., an event that may not be immediately life-threatening or result in death or hospitalization but, based upon appropriate medical and scientific judgment, may jeopardize the patient or may require medical or surgical intervention to prevent one of the other serious outcomes listed above.
 - Examples of important medical events include, but are not limited to, intensive treatment in an emergency room or at home for allergic bronchospasm, blood dyscrasias, or convulsions. Interruption, discontinuation, or adjustment of dose level of study drug alone will not be considered an intervention that satisfies the definition of important medical event.

Although fulfilling the above listed criteria, the following events are not regarded as being serious for this study:

Hospitalizations for:

- Facilitation of assessments specific to this protocol not associated with any deterioration in condition (e.g., when travel time between a patient's home and the study site would otherwise preclude adequate evaluation).
- Elective or preplanned assessment or treatment for a preexisting condition that has not worsened since initiation of study drug administration.

Any SAE meeting above criteria that occurs during the study or within 4 weeks after the last dose of study drug must be reported within 24 hours (1 working day) by email and/or fax and by completing the AE electronic case report form (eCRF) and the SAE Report Form. Once the AE eCRF is completed designating an AE as serious, an email will be generated to notify and that an SAE has occurred and the information will be transmitted to the designated parties for review.

Confidential Page 6 of 195

Refer to additional SAE reporting instructions in **Section 9.2**.

FINAL, 13 October 2017 TOZ-CL05, Amendment No. 3

CLINICAL STUDY PROTOCOL SIGNATURE PAGE

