9.2.2 Procedures for Reporting Serious Adverse Events

If an SAE is reported, the Sponsor must be informed within 24 hours of receipt of this information by the site (see contact information for SAE reporting listed in the Serious Adverse Event Reporting section at the front of the protocol). An SAE Report Form will be provided to the investigator. The SAE Report Form must be completed in English.

The investigator must forward to the Sponsor (or its representative) a duly completed SAE Report Form provided by the Sponsor, even if the data are incomplete, or if it is obvious that more data will be needed in order to draw any conclusions. Information recorded on this form will be entered into the global safety database.

It is important for the investigator, when completing the SAE Report Form, to include the assessment as to a causal relationship between the SAE and the IMP administration. This insight from the investigator is very important for the Sponsor to consider in assessing the safety of the IMP and in determining whether the SAE requires reporting to the regulatory authorities in an expedited manner.

Additional information (e.g., autopsy or laboratory reports) received by the investigator must be provided within 24 hours. All documents in the local language must be accompanied by a translation in English, or the relevant information included in the same document must be summarized in the SAE Report Form.

The investigator is specifically requested to collect and report to the Sponsor (or its representative) any SAEs (even if the investigator is certain that they are in no way associated with the IMP) up to 4 weeks from the date of last IMP for each patient, and to also inform participating patients of the need to inform the investigator of any SAE within this period. Serious AEs that the investigator thinks may be associated with the IMP must be reported to the Sponsor regardless of the time between the event and the end of the study.

Upon receipt of the SAE Report Form, the Sponsor will perform an assessment of expectedness of the reported SAE. The assessment of the expectedness of the SAE is based on the current IB.

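### The important-medical-event test for an SAE joins its two limbs with *or* in the protocol's front section but with *and* in Section 9.2.1, and the front section's one-working-day gloss loosens the 24-hour reporting clock

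*Protocol*

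**What the plan says.** **Definition.** In the SAE reporting section at the front of the protocol, criterion 6 makes an event an important medical event if it "may jeopardize the patient or may require medical or surgical intervention to prevent one of the other serious outcomes listed above". Section 9.2.1, item 5, requires that it "may jeopardize the patient and may require medical or surgical intervention to prevent one of the other outcomes" in the list. Both leave the decision to medical judgment.

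**Stopping drug.** Only the front section adds that "discontinuation, or adjustment of dose level of study drug alone will not be considered an intervention" for this purpose. Section 9.2.1 has no such sentence.

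**Examples.** The front section gives "intensive treatment in an emergency room or at home for allergic bronchospasm, blood dyscrasias, or convulsions". The note in Section 9.2.1 lists "blood dyscrasias that do not result in inpatient hospitalization", with no condition about treatment.

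**Clock.** The front section says an SAE "must be reported within 24 hours (1 working day) by email and/or fax", and that sentence gives no starting point. Section 9.2.2 says "the Sponsor must be informed within 24 hours of receipt of this information by the site". Section 9.3 asks for SAEs to be reported immediately.

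**Precedence.** The front section sends the reader to Section 9.2 for additional instructions, and Section 9.2.2 sends the reader back to the front section for contact details. Neither says which wording prevails.

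**The concern.** Seriousness decides the reporting route. Section 9.2.1 closes by saying that seriousness, not severity, guides regulatory reporting obligations. Section 9.3 limits immediate reporting to SAEs and suspected transmission of an infectious agent. Under Section 9.2.2 the SAE form feeds the global safety database and the decision on expedited reporting. The Medical Monitor's ongoing review in Section 9.1.8 is a review of SAEs, and SAP Section 9.7.2 tabulates serious TEAEs by system organ class and preferred term.

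If two sites use different pages of the same protocol, they can classify the same event differently, each following the text as written. At stake are the consistency of SAE counts and the timeliness of expedited reports. The efficacy analysis is not involved.

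**Working it through.** The plan gives no figure to reproduce here. Two checks apply: the logic of the two definitions, and the arithmetic of the clock.

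**1. Logic of the definitions.** Let J mean that the event may jeopardize the patient, and M that it may require a medical or surgical intervention other than stopping study drug.

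- Front section: serious if J or M.
- Section 9.2.1, read literally: serious if J and M.

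| J | M | Front section | Section 9.2.1 | Agree? |
|---|---|---|---|---|
| no | no | not serious | not serious | yes |
| no | yes | serious | not serious | no |
| yes | no | serious | not serious | no |
| yes | yes | serious | serious | yes |

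The tests disagree in 2 of 4 combinations. In both, the event is serious under the front section and not under 9.2.1. This must be so, because any event that satisfies J and M also satisfies J or M.

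Now take a patient whose drug has been stopped, and suppose that a site using 9.2.1 counts the stop as an intervention, which that section does not forbid. The J-only row becomes serious on both pages, and disagreement falls to 1 of 4 (M only). It never falls to zero.

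These are counts of logical cases, not of expected events. The documents give no basis for estimating how many events would meet only one limb.

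**2. Clock.** Assume a Monday-to-Friday working week and awareness at the site on Friday at 17:00.

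- 24 hours from receipt (Section 9.2.2): Friday 17:00 + 24 h = Saturday 17:00.
- One working day (the front section's gloss): Monday 17:00, which is 3 × 24 = 72 h after awareness.
- Difference: 72 − 24 = 48 h.

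For awareness from Monday to Thursday the two readings coincide, apart from public holidays.

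**The case against.** **Two stronger readings are tempting, and the documents support neither.**

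*Neutropenia.* A reader might infer that an asymptomatic absolute neutrophil count below 1000/mm³, which Section 4.3.2 makes a reason for withdrawal, is an SAE on one page and not on the other. That result needs the front section's sentence on stopping drug to be carried into Section 9.2.1, where it does not appear. Read alone, 9.2.1 names non-hospitalized blood dyscrasias as an example of an important medical event, which points towards serious. Its second limb is also prospective: an event may require intervention even if none has yet been given. A split is possible but does not follow automatically.

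*Clock.* A reader might infer that one page says 24 hours and the other says one working day. Both say 24 hours. The looseness lies inside the front section's own sentence. A site reaches 72 hours only by following the parenthesis rather than the figure it qualifies, and Section 9.3's demand for immediate reporting weighs against doing so.

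**Consequence.** The hematologic signal does not depend on SAE status. Section 4.3.2 requires withdrawal, weekly hematology, adverse event assessment and discussion with the medical monitor for a count below 1000/mm³, whether or not it is called serious. Clinically significant laboratory findings are recorded as adverse events (Protocol Section 11.5.1). The SAP tabulates adverse events leading to discontinuation (9.7.1) and hematology shifts to the worst post-baseline value (9.7.3).

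**What stands.** These arguments narrow the point without removing it. The two conjunctions differ in current operative text, medical judgment is exercised against whichever criterion the site reads, and the parenthesis permits a reading that 9.2.2 excludes. The blood-dyscrasia note also sits awkwardly with a literal *and* in its own section, which is a further reason to reconcile the wording.

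**Conclusion.** The inconsistency is real and should be corrected. An event that meets exactly one limb of the important-medical-event criterion is an SAE under the front section and not under a literal reading of Section 9.2.1. The error has one direction: sites working from 9.2.1 can only classify fewer events as serious. Separately, the front section's gloss can be read as giving up to 72 hours over an ordinary weekend where 9.2.2 gives 24.

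The effect is confined to SAE classification, expedited reporting and the serious TEAE table. Primary and secondary efficacy results, the significance level and the sample size are untouched, and low neutrophil counts still reach the medical monitor under Section 4.3.2.

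The conclusion assumes that 9.2.1 is read literally and, for the clock, a Monday-to-Friday working week. Criteria 1 to 4 of the front section's list were not available for this review, so only the important-medical-event criterion could be compared. That is a limit of the review, not a fault in the protocol.

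**What to change.** Reconcile the front SAE section with Sections 9.2.1, 9.2.2 and 9.3 so that the protocol has one definition and one clock.

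- **Definition.** Use the same conjunction in both places. The broader *or* captures every event that either page captures and fits the blood-dyscrasia example already in 9.2.1. In practice this is one word in 9.2.1, item 5.
- **Clock.** Delete the one-working-day parenthesis from the front section. State in both places that the 24 hours run from receipt of the information by the site, and align the immediate-reporting wording in 9.3 with that.

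No extra sentence on drug discontinuation is needed. Once both pages say *or*, the jeopardy limb stands on its own, and the existing front-section sentence limits only what counts as an intervention.

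The cost is a few wording changes and possibly a few more events reported as serious. Weekend reporting is not a new burden, because Section 9.2.2 already sets 24 hours.

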9.2.2 Procedures for Reporting Serious Adverse Events

If an SAE is reported, the Sponsor must be informed within 24 hours of receipt of this information by the site (see contact information for SAE reporting listed in the Serious Adverse Event Reporting section at the front of the protocol). An SAE Report Form will be provided to the investigator. The SAE Report Form must be completed in English.

The investigator must forward to the Sponsor (or its representative) a duly completed SAE Report Form provided by the Sponsor, even if the data are incomplete, or if it is obvious that more data will be needed in order to draw any conclusions. Information recorded on this form will be entered into the global safety database.

It is important for the investigator, when completing the SAE Report Form, to include the assessment as to a causal relationship between the SAE and the IMP administration. This insight from the investigator is very important for the Sponsor to consider in assessing the safety of the IMP and in determining whether the SAE requires reporting to the regulatory authorities in an expedited manner.

Additional information (e.g., autopsy or laboratory reports) received by the investigator must be provided within 24 hours. All documents in the local language must be accompanied by a translation in English, or the relevant information included in the same document must be summarized in the SAE Report Form.

The investigator is specifically requested to collect and report to the Sponsor (or its representative) any SAEs (even if the investigator is certain that they are in no way associated with the IMP) up to 4 weeks from the date of last IMP for each patient, and to also inform participating patients of the need to inform the investigator of any SAE within this period. Serious AEs that the investigator thinks may be associated with the IMP must be reported to the Sponsor regardless of the time between the event and the end of the study.

Upon receipt of the SAE Report Form, the Sponsor will perform an assessment of expectedness of the reported SAE. The assessment of the expectedness of the SAE is based on the current IB.

9.2.3 Follow Up of Serious Adverse Events

An SAE will be followed until it has resolved, has a stable sequelae, the investigator determines that it is no longer clinically significant, or the patient is lost to follow up.

Information on SAEs obtained after clinical database lock will be captured through the global safety database without limitation of time.

9.3 Immediate Reporting of Adverse Events

The following AEs must be reported immediately:

- SAE: AE that the investigator classifies as serious by the above definitions regardless of causality.
- Suspected transmission of an infectious agent via a medicinal product.

9.4 Laboratory Measurements

The laboratory tests listed below (**Table 4**) are to be performed and analyzed as outlined in the Schedule of Events/Evaluations (**Table 1** and **Table 2**).

Sample collection kits and the laboratory procedures manual with detailed sample processing and shipping instruction will be provided by the accredited central laboratory.

All laboratory samples will be destroyed upon authorization by the Sponsor or Sponsor's designee, at the finalization of the clinical study report.

The following laboratory parameters will be measured:

Table 4: Laboratory Measurements

Hematology	Chemistry	Thyroid	Urinalysis ^b
Basophils	AST	TSH	Protein
Eosinophils	ALT	Free T ₃	Glucose
Hematocrit	ALP	Free T ₄	pН
Hemoglobin	Albumin	Thyroperoxidase antibody (screening only)	Blood
Lymphocytes	Bicarbonate		Ketones
Monocytes	Calcium		Specific gravity
Neutrophils	Chloride		Urine pregnancy test (females of childbearing potential, only)
Platelet count RBC count WBC count	Creatine phosphokinase with automatic Troponin-I and CK-MB if value > 2 x the ULN		
	Creatinine		
	Glucose		
	GGT		
	LDH		
	Phosphate		
	Potassium		
	Sodium		
	Total bilirubin ^a		
	Total cholesterol		
	Total protein		
	Urea/BUN		
	Uric acid		
	Follicle stimulating hormone (females postmenopausal <2 years, only)		

ALP, alkaline phosphatase; ALT, alanine transaminase; AST, aspartate transaminase; BUN, blood urea nitrogen; CK-MB, creatine phosphokinase-MB; GGT, gamma-glutamyl transpeptidase; LDH, lactate dehydrogenase; pH, reverse logarithmic representation of relative hydrogen proton (H+) concentration; RBC, red blood cell; T3, triiodothyronine; T4, thyroxine; TSH, thyroid stimulating hormone; ULN, upper limit of normal; WBC, white blood cell.

9.5 Other Safety Measurements

9.5.1 Blood Pressure and Pulse Measurements

Blood pressure and pulse rate should be obtained in a quiet room at a comfortable temperature, with the patient's arm unconstrained by clothing or other material. A full set of measurements will include BP and pulse obtained after at least 5 minutes supine rest, followed by BP and pulse obtained after the patient has been standing for approximately 1 and 3 minutes. At Screening and Baseline (Visit 2), the full set of BP and pulse measurements will be collected on 3 occasions approximately 10 minutes apart. If repeats are performed for either supine or standing BP, the

^a Conjugated and unconjugated.

^b If urine dipstick is positive for leukocytes, protein, or erythrocytes, a microscopic evaluation and culture will be performed.

full set (BP and pulse) should be repeated after 5 minutes supine rest (i.e., supine followed by standing measurements). The measurements will be obtained throughout the study using an appropriate cuff size from the patient's non-dominant arm. If possible, all measurements for a given patient will be obtained from the same arm using the same cuff. The cuff should be placed on the designated arm at least 5 minutes prior to collection. If available, an automatic BP cuff (sphygmomanometer) with a digital readout will be used.

Supine and standing systolic and diastolic BP and pulse rate will be recorded at the nominal time points specified in the Schedule of Events/Evaluations (**Table 1** and **Table 2**). If, for any reason, an accurate reading cannot be obtained (e.g., dyskinesia), collect the measurement as close to the nominal time point as feasible and record the date and time of collection.

Patients noted to have an elevated BP post-baseline, with a systolic BP \geq 160 mmHg and/or a diastolic BP \geq 100 mmHg that is present at 2 consecutive post-baseline study visits, will be discontinued from study (see Section 4.3.2).

9.5.2 Twelve-lead Electrocardiogram (ECG)

A resting supine 12-lead ECG will be collected at the time points specified in the Schedule of Events/Evaluations (**Table 1** and **Table 2**) after the patient has been in a supine position for a minimum of 5 minutes.

The 12-lead ECG includes standard PR, QRS, QT and QTc (heart rate-corrected QT) intervals as read by the ECG machine provided by the cardiac core lab. Fridericia's correction (QTcF) must be used for correction of the QT interval.

A central ECG core lab will overread all ECGs and provide the final interpretation. At Screening the results will be available within 72 hours of the visit. At Baseline, the overread of the 3 serial ECGs will be available within 24 hours. The investigator should use the ECG-recorded QTcF interval to meet eligibility requirements.

